6. STATISTICAL SOFTWARE AND QUALITY CONTROL

6.1 Software

- **Main program:** SPSS version 30.0
- **Add-on software:** Microsoft Excel for data management
- **Version control:** Daily database backup

6.2 Planned Data Quality Control

- **Programmed double keying:** For 10% of randomly selected data
- **Systematic Range Checking:** Identifying Values Outside Expected Ranges
- **Protocolized Internal Consistency:** Checking for Consistency Between Related Variables
- **Outlier detection:** Identification by preset Tukey method ($IQR \times 1.5$)

6.3 Planned Analysis Documentation

- **SPSS Syntax:** Preset Command File to Use
- **Output Log:** Scheduled documentation of all statistical outputs
- **Methodological decisions:** Systematic recording of all decisions according to protocol

7. ADDITIONAL SENSITIVITY ANALYSIS

7.1 Analysis by Planned Exploratory Subgroups

- **Age:** Programmed comparison between group 3-5 years vs. 6-7 years.
- **Diagnosis:** Pre-established ASD vs. other DNDs.
- **Adherence:** Planned comparison $\geq 80\%$ vs. $< 80\%$ of completed sessions.

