5. PARTICIPANTS

5.1 Target Population

Universe: Children aged 3-7 years with ASD and other associated DNDs who attend Sentido's Therapy Organization CAIP&CICI (Comprehensive Pediatric Care Center and Intensive Behavioral Intervention Center), Comodoro Rivadavia, Chubut, Argentina.

Sample: All eligible childhoods during the study period.

Selection: Non-probabilistic convenience, non-random, voluntary.

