5.2 Eligibility Criteria

Inclusion Criteria:

1. **Informed consent signed** by the parent or guardian.
2. **Comply with the requirements** for executive admission.
3. **Meet the DSM-V** diagnostic impression criteria for neurodevelopmental disorders:

- Intellectual disability (ID); developmental global delay (MDR) or psychomotor delay (RPM).
 - Communication disorders: language disorders (SL), speech disorders, social communication disorder (SCD), childhood-onset dysfluency.
 - Autism spectrum disorder (ASD).
 - Attention deficit hyperactivity disorder (ADHD).
 - Motor developmental disorders: developmental coordination disorder (BDD), stereotypic movement disorder, tic disorders, Tourette's disorder (TT), chronic tic disorder (TT), transient tic disorder
 - Specific learning disorders (PAC).
4. **Respond to the GAS, Vineland-3 and FOS scales** in therapeutic admission.
 5. **Willingness of significant caregivers** to accompany in the intervention process, for twelve sessions according to the syllabus protocol.

Exclusion Criteria:

1. **Childhoods that exceed the age of 7 years** in the period of study.
2. **Children diagnosed with neurological or genetic diseases**, brain injury, visual, auditory or motor sensory deficits.
3. **Children who are under the guardianship of the Argentine State.**

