2.2 Population Analysis

Target population: n = 24 estimated participants who meet inclusion criteria and complete evaluations in the three planned time points.

Pre-established criteria for inclusion in analysis:

- Participants aged 3-7 years with a confirmed diagnosis of ASD and/or associated DND according to DSM-V
- Signed informed consent
- Completion of the 14-week intervention protocol
- Complete data in the three temporary evaluations

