3.3 Characterization Variables

- Age (full years at admission).
- Sex (male/female).
- Primary diagnosis (associated ASD, DND).
- Adherence to the protocol (percentage of completed sessions).

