10. RECOGNIZED STATISTICAL LIMITATIONS

10.1 Design Limitations

- **Absence of a control group:** Limitation for causal inferences.
- **Intrasubject design:** Possible effects of practice or time.
- **Sample size:** n=24 limits statistical power for subgroup analysis.

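### SAP 7.1 compares children aged 3-5 with those aged 6-7 without a reason for the cut; a continuous-age slope would use the 24 children better (minor, exploratory)

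*Combined protocol and SAP*

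**What the plan says.** SAP 7.1, headed "Analysis by Planned Exploratory Subgroups", lists three subgroup factors: age, diagnosis and adherence. For age it gives "Programmed comparison between group 3-5 years vs. 6-7 years". It names no outcome, model or interaction test for the comparison, and no section explains why the boundary falls between 5 and 6.

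SAP 3.3 lists age in completed years at entry ("Age (full years at admission"). No other age variable appears, and neither date of birth nor age in months is mentioned.

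SAP 2.2 expects 24 "estimated participants who meet inclusion criteria and complete evaluations in the three planned time points". SAP 10.1 acknowledges that "n=24 limits statistical power for subgroup analysis".

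Protocol 5.1 defines the population as "Children aged 3-7 years with ASD and other associated DNDs", and Protocol 5.2 excludes "Childhoods that exceed the age of 7 years". Neither section, nor any other, describes the expected spread of ages.

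**The concern.** Age is a graded quantity. Reducing it to two groups treats a child of 3 like a child of 5, and puts children of 5 and 6 on opposite sides. If change varies gradually with age, part of that variation is discarded and the result depends on where the cut falls. The two groups are also uneven in width, with three year-bands against two.

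The SAP itself recognises that power for subgroup work is limited at this sample size, so a choice that gives up more precision needs a reason, and none is given. What is at stake is modest: how well the trial can say whether change depends on age. Neither the primary nor any secondary conclusion is affected.

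**Working it through.** The documents give no figure for information loss or subgroup power, so there is nothing of theirs to reproduce.

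**Inputs from the documents.** The cut at 6 years (SAP 7.1); whole-year age (SAP 3.3); n = 24 (SAP 2.2); ages 3-7 (Protocol 5.1); two-sided 0.05, which SAP 4.5.1 states for the primary analysis and is borrowed here for illustration.

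**Assumptions.** A linear relation between age and change, and the age distributions named below.

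**Step 1: split against exact age.** The share of linear age information kept is r², the squared correlation between age and the 6-7 indicator. For age uniform on an interval of width w, with share p aged 6 or over:
- covariance = w·p(1−p)/2
- variance of age = w²/12
- variance of the indicator = p(1−p)
- hence r² = 3p(1−p)

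For ages from 3.0 to under 8.0, p = 2/5 = 0.40, so r² = 3 × 0.40 × 0.60 = 0.72. The loss is 28%, equivalent to 24 × 0.72 = 17.3 children.

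**Step 2: split against whole-year age.** With ages 3, 4, 5, 6 and 7 equally likely, the variance is 2 and the covariance with the indicator is (6 + 7)/5 − 5 × 0.40 = 0.6. Then r² = 0.36/(2 × 0.24) = 0.75. The loss is 25%, equivalent to 24 × 0.75 = 18 children.

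**Step 3: rounding alone.** Whole-year age keeps 2/(25/12) = 0.96 of the information in exact age. The parts agree: 0.96 × 0.75 = 0.72.

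**Step 4: other age distributions.**

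| Assumed ages | r² | Loss |
|---|---|---|
| Whole years, U-shaped (3:2:1:2:3) | 0.84 | 16% |
| Whole years, skewed old (1:2:3:4:5) | 0.76 | 24% |
| Whole years, even | 0.75 | 25% |
| Exact, even over 3.0 to under 8.0 | 0.72 | 28% |
| Whole years, peaked at 5 (1:2:3:2:1) | 0.67 | 33% |
| Whole years, skewed young (5:4:3:2:1) | 0.64 | 36% |
| Whole years, 3-6 only, even | 0.60 | 40% |
| Whole years, strongly skewed young (8:7:5:3:1) | 0.59 | 41% |
| Exact, even over 3.0-7.0 (strict upper limit) | 0.56 | 44% |

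Even if ages are truly uniform from 3.0 to under 8.0, chance variation in a sample of 24 gives a 95% range of about 15% to 44% (20,000 simulated samples).

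**Step 5: power under the even spread.** Fisher-z power is Φ(√(n−3)·atanh(r) − 1.96), with √21 = 4.583. For the split, r is multiplied by √0.72.
- True correlation 0.5, exact age: 4.583 × 0.549 − 1.96 = 0.557, power 71%.
- Same correlation, split: r = 0.424; 4.583 × 0.453 − 1.96 = 0.116, power 55%.
- Same method for 0.3: 29% against 22%; 0.4: 49% against 37%; 0.6: 89% against 73%.

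A noncentral-t calculation for 0.5 gives 77% with exact age, 75% with whole-year age and 59% with the split. The levels are somewhat higher and the gap is similar.

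**The case against.** Several counter-arguments have force.

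- **No single percentage is a fact about this trial.** The 28% needs an even spread of exact ages. The upper age limit is also unclear: if it must hold throughout each child's 17 weeks (17/52 = 0.33 years), entry ages stop near 7.67 or 6.67. Under uniform ages p is then 0.36 or 0.18, and the loss about 31% or 55%. This stands: the figure must be given as conditional, and 15-44% is a working range, not a bound.
- **Part of the 28% is rounding.** This stands. Against the age variable the SAP actually lists, the even-spread loss is 25%.
- **A split assumes no straight line and would capture a real step at 6.** This stands, so the split cannot be called worthless. But the SAP gives no reason to expect a step there, and a scatter plot with the group means would still show one.
- **Both analyses are weak for modest relations.** At a correlation of 0.3, power is 29% against 22%, so the change does not rescue the question. That is true, and it favours an estimate with an interval over a two-group contrast.
- **The analysis is exploratory and tied to no stated objective.** This stands and sets the severity.
- **SAP 7.1 has a wider gap.** No subgroup comparison has a named outcome or model, and adherence is split too, at 80%. This is fair. It does not remove the point about age, and the fix supplies what is missing there.

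A reader might infer that the SAP formally tests whether age modifies the effect, or admits that the analysis is underpowered. It does neither: it plans a comparison and says only that the sample size "limits statistical power for subgroup analysis". A reader might also infer that exact age is already held for every child. The documents list only completed years.

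**Conclusion.** The point holds as a minor, cheap improvement. The cut is unexplained, no continuous-age analysis is planned, and a two-group comparison gives up precision on a linear age effect under every age distribution examined. The size depends on two assumptions the documents cannot settle: how ages are distributed and whether the relation is roughly linear. Under an even spread, the power difference at a true correlation of 0.5 is about 16 percentage points (71 − 55) if exact age is available. The documents do not support any suggestion that the trial's main conclusions are weakened.

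**What to change.** In SAP 7.1, replace the age-group comparison with a regression of the week 0 to 17 ABC change (the primary variable in SAP 3.1) on age as a continuous variable. Report the slope with a 95% interval and a scatter plot. Keep the 3-5 and 6-7 means as a descriptive table only.

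In SAP 3.3, record age at admission in months if date of birth is on file. If it is not, use whole years, which recovers most of the gain.

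The cost is a few lines of SAP wording, with no change to visits or instruments; months need no new data only if dates of birth are held. The downside is that a linear age effect is assumed and can be checked only roughly with 24 children.

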7.2 Scheduled Influential Case Analysis

- **Pre-established methods:** Cook distance, standardized residuals.
- **Predefined criteria:** Values > 3 SD considered atypical.
- **Planned analysis:** Repetition of main analyses excluding influential cases according to protocol.

8. HANDLING DEVIATIONS FROM THE PLAN

8.1 Minor deviations

- Adjustments to assumption verification methods.
- Changes in graphical methods of presentation.

- **Documentation:** In statistical report.

8.2 Major deviations

- Changes in primary analysis methods.
- Modifications in variable definitions.
- **Approval:** Required from the principal investigator.
- **Documentation:** Protocol amendment.

9. STATISTICAL ANALYSIS SCHEDULE

9.1 Data Cleansing Phase (Week 1-2)

- Completeness and consistency verification.
- Identification and resolution of discrepancies.
- Final database preparation.

9.2 Descriptive Analysis Phase (Week 3)

- Basal characteristics.
- Verification of statistical assumptions.

9.3 Inferential Analysis Phase (Week 4-5)

- Primary variable analysis.
- Analysis of secondary variables.
- Sensitivity analysis.

9.4 Interpretation Phase (Week 6)

- Synthesis of results.
- Preparation of tables and figures.
- Statistical report writing

10. RECOGNIZED STATISTICAL LIMITATIONS

10.1 Design Limitations

- **Absence of a control group:** Limitation for causal inferences.
- **Intrasubject design:** Possible effects of practice or time.
- **Sample size:** n=24 limits statistical power for subgroup analysis.

10.2 Instrument Limitations

- **Local validation:** Vineland-3 and FOS not validated in the Argentine population.
- **Interpretation:** Caution required in absolute magnitudes.
- **Strategy:** Focus on consistent patterns of change.

10.3 Considerations of Multiple Comparisons

- **Secondary variables:** Increase in type I error without global adjustment.
- **Interpretation:** Secondary outcomes such as exploratory/hypothesis generators.

ANNEXES

